2.3. Sample Size and Power Considerations

The sample size will be approximately 315 patients per arm, for a total of 630 patients in two treatment groups. This study is powered to detect the difference between REGN1908-1909 and placebo on the primary endpoint of daily CSMS averaged over the last 12 weeks of the treatment period (weeks 48 to 60) when considering a 20% dropout rate by week 60.

A sample size of 251 patients per arm gives 90% power to detect a mean difference in daily CSMS, averaged over weeks 48-60, of 1.8 (20% reduction from placebo) between REGN1908-1909 (mean CSMS=7.3) and placebo (mean CSMS=9.1), assuming a common standard deviation in CSMS of 6.2. Assuming a 20% dropout rate (~64 per arm), the sample size is 315 per arm. A 2-sample t-test with 2-sided alpha of 0.049 was assumed (an administrative penalty of 0.001 will be taken from the significance level used at final analysis due to a planned interim analysis; details are provided in Section 7). Calculations were performed using nQuery+nTerim 4.0.

The sample size of 315 patients per arm also gives the power of 91% and 96% to detect a 20% reduction from placebo in TSS (SD=3.0 and mean in placebo=4.2) and daily TNSS (SD=2.3 and mean in placebo=3.3) averaged over the last 12 weeks (weeks 48 to 60), respectively. Details are displayed in Table 1.

Table 1: Summary of Statistical Assumptions and Power for Select Secondary Endpoints

Daily Score, Averaged over last 12 weeks	Mean		Anti-Fel d 1 vs Placebo		Power with n=315/arm*	Power with n=251/arm*
	Placebo	Anti-Fel d 1	% Reduction from Placebo	Reduction from Placebo (SD)		
TNSS	3.3	2.6	-20%	-0.7 (2.3)	96%	92%
TSS	4.2	3.4	-20%	-0.8 (3.0)	91%	84%

*: Two-sided t-test with alpha = 0.049, assuming 20% reduction from PBO

The assumptions of mean in the placebo and common standard deviation for the above endpoints are based on the house dust mite (HDM) SLIT-tablet data for combined rhinoconjunctivitis score during 8-week assessment period. A treatment difference of 20% relative to placebo is based on a previous phase 1b study (R1908-1909-ALG-1325) of the same molecules and the treatment effect observed for reduction in symptoms after a nasal allergen challenge over a 12-week period.

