
Endpoint Category	Estimand			
	Endpoint(s)	Population	Intercurrent event(s) handling strategy and missing data handling	Population-level summary
			
analysis (treatment policy); otherwise, for travel \geq 42 consecutive days, a hypothetical strategy will be used where data during patient travel will be set to missing
 
In addition, the missing data imputation rules for patients who have no available values of CSMS⁴ during the last 12 weeks of the treatment period are as follows:
 
 Missing data due to patients' discontinuation from study due to AEs and lack of efficacy will be imputed using worst average CSMS score during the last 12 weeks of all observations in the corresponding treatment group Missing data due to any other reason will be imputed using MI 	

[1] If a data point or missing value falls into multiple categories of intercurrent events as specified above, the following priority order for handling of data will be applied: ICE 3), ICE 4), ICE 5b) ICE 5a), ICE 1), ICE 2). For example, if data or missing value fall into both ICE 3) and 5a), the strategy for ICE 3) should be followed, as it takes priority over 5a).
 
[2] Select prohibited medications that will be handled using a treatment policy are listed in Category 1 of Table 7
 
[3] Additional prohibited medications listed in Category 2 Table 7 will undergo blinded adjudicated by study medical monitor before the database lock to determine if they will be handled by treatment policy, composite strategy, or hypothetical strategy
 
[4] No available values of CSMS means no available TNSS, TOSS, or DMS during the last 12 weeks of the efficacy assessment period
				

The primary analysis will focus on the comparison between REGN1908-1909 and placebo in the FAS. The analysis will be performed using an analysis of covariance (ANCOVA) model, with the treatment group, randomization stratification factors (as stratified), and cat sIgE (<17.5 kUa/L versus ≥ 17.5 kUa/L) as fixed effects and the baseline CSMS as a covariate. The baseline CSMS will be calculated as the average CSMS during the first 15 consecutive days of the baseline assessment period where eligibility criteria (for TSS and rescue medication use) were met, as specified based on the following two criteria:

1. Must have at least 8 unique days of a TSS score ≥ 8 within a 15 consecutive day period.

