2. Must have a least 8 unique days of a DMS score >0 within the same 15 consecutive day period as Criteria 1. The 8 unique days do not have to occur on the same days as Criteria 1; however, they must be within the same 15 consecutive days.

If less than 15 days of data are available during the baseline assessment period, the baseline will be the average CSMS over all available days (if duplicate entries of CSMS are available on the same day, the worst score will be used).

Only days with observed data will be included in the calculation of average score. The average CSMS (max score 38/day) will be calculated based on the sum of average daily TNSS (max score 12/day), average daily TOSS (max score 6/day) and average daily medication scores (DMS, max of 20/day) recorded over the last 12 weeks of the treatment period (weeks 48 to 60).

For the MI procedure, missing data (the average CSMS) will be imputed 50 times to generate 50 complete data sets utilizing the SAS procedure PROC MI. Note that any imputation by worst CSMS score as specified in [Table 4](#) will occur prior to MI. The 2 steps below will be followed for MI:

Step 1: The Markov Chain Monte Carlo (MCMC) method will be used to fill in missing values of average CSMS during weeks 0-12 by treatment group so that a monotone missing pattern will be formed.

Step 2: Using the data sets from Step 1, missing values of average CSMS from weeks 48-60 will be imputed using a monotone regression method. The imputation model will include the covariates in the ANCOVA model and the average CSMS from weeks 0-12.

For steps 1 and 2, any score imputed outside the range of CSMS (0-38) will be truncated to the nearest value of CSMS according to the following algorithm:

- If the imputed score > 38, then the final imputed score will be 38.
- If the imputed score < 0, then the final imputed score will be 0.

Sample SAS syntax code for MI:

```
proc mi data=mi1 out=mi3 noint nimate=50 seed=190819;
mcmc impute=monotone;
var BASELINE CSMS012 CSMS4860;
by TRTP;
run;

proc mi data=mi3 out=mi4 nimate=1 seed=190819;
class TRTP STRAT1 STRAT2 STRAT3 CATIGE;
monotone reg;
var TRTP STRAT1 STRAT2 STRAT3 CATIGE BASELINE CSMS012;
by _imputation_;
run;
```

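### Arm-worst scores are filled in before multiple imputation, so the model for all other missing patients is fitted to assigned extremes: imputed values rise and the primary standard error widens by about 2-7%

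*SAP*

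**What the plan says.** SAP 5.6.1, Table 4, treats patients with no CSMS in weeks 48-60 in two ways. Those who left the study for an adverse event or lack of efficacy "will be imputed using worst average CSMS score during the last 12 weeks of all observations in the corresponding treatment group". For the rest: "Missing data due to any other reason will be imputed using MI". The arm-worst average also goes to intercurrent event (ICE) 3b: prohibited medication adjudicated to the composite strategy, with no earlier score in the period. ICE 3a is different. It carries the patient's own worst score forward from the day of the medication.

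The text below Table 4 sets the sequence: "Note that any imputation by worst CSMS score as specified in [Table 4](#) will occur prior to MI". Step 1 then runs MCMC by arm to make the pattern monotone. Step 2 is a regression on the ANCOVA covariates and the weeks 0-12 average. Neither step excludes or flags filled rows, and the Step 1 sample code lists the weeks 48-60 average among its variables. The tipping-point analysis repeats both steps and describes δ=0 as the standard missing-at-random analysis.

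Protocol 11.4.3.1 describes the hybrid of worst score and multiple imputation (MI) without giving an order.

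**The concern.** Under missing at random, imputed values should be drawn from the outcomes of comparable patients who were observed. Here the regression also sees a block of identical values at the arm maximum, unrelated to those patients' baseline or weeks 0-12 scores. The block raises the fitted mean and inflates the residual variance, and both carry into the draws for patients who left for other reasons. Step 2 is one regression with a common residual variance, so extreme fills in one arm also widen the draws in the other.

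Table 4 deliberately separates the two kinds of leaver. The sequence partly undoes that, because the penalty assigned to one group helps to set the values of the other. At stake are precision of the primary contrast, the arm means, and the starting point of the tipping-point analysis, whose δ=0 run already carries an undeclared upward shift. None of the listed sensitivity or supplemental analyses states that MI is to be fitted to observed averages only.

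**Working it through.** **1. The plan's own figure.** SAP 2.3 states: "A sample size of 251 patients per arm gives 90% power to detect a mean difference in daily CSMS", a difference "of 1.8 (20% reduction from placebo) between REGN1908-1909 (mean CSMS=7.3) and placebo (mean CSMS=9.1"), "assuming a common standard deviation in CSMS of 6.2". It adds: "A 2-sample t-test with 2-sided alpha of 0.049 was assumed".

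n per arm = 2 × (1.969 + 1.282)² × (6.2/1.8)² = 250.7, so 251. Inflating for dropout, 251/0.80 = 313.75, so 314. The SAP says "Assuming a 20% dropout rate (~64 per arm), the sample size is 315 per arm", which agrees within rounding.

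**2. Hand check of the shift.** Let a fraction f of each arm be filled and 80% observed. The filled rows make up f/(f + 0.80) of the fitted data, so the fitted mean rises by about

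shift ≈ f/(f + 0.80) × (arm maximum − mean).

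- Right-skewed scores: maximum about 34.8, mean 8.2, gap 26.6. At f = 1%, 0.0123 × 26.6 = 0.33. At 2%, 0.0244 × 26.6 = 0.65. At 5%, 0.0588 × 26.6 = 1.56.
- Truncated-normal scores: maximum about 25.6 (mean of the arms), mean 8.5, gap 17.1. The shifts are 0.21, 0.42 and 1.01.

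Truncating draws to 0-38 adds a little more: with a wider residual SD, more draws fall below zero and are moved up to it.

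**3. Simulation.** From the documents: 315 per arm, means 9.1 and 7.3, SD 6.2, 20% missing, 50 imputations, truncation to 0-38, two-sided 0.049, and the ANCOVA and imputation covariates of SAP 5.6.1. Assumed, because the documents do not say:

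- 1-5% of each arm is filled;
- correlations are 0.5 with baseline and 0.7 between the two periods;
- scores are truncated normal or gamma;
- weeks 0-12 data are complete, and missingness is completely at random.

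There were 400 trials per scenario, so a power figure has a standard error of up to about 2 points. The second PROC MI variable list, as printed, omits the weeks 48-60 average; the simulation follows the Step 2 text, which says it is imputed there.

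SAP order against MI on observed averages followed by insertion of the worst scores, equal fills:

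| Scores | Filled | Net shift in imputed values | SE, SAP order | SE, reversed | Change | Power, SAP order | Power, reversed |
|---|---|---|---|---|---|---|---|
| Normal | 1% | +0.23 | 0.450 | 0.440 | +2.1% | 94.8% | 94.8% |
| Normal | 2% | +0.46 | 0.475 | 0.459 | +3.5% | 93.5% | 94.8% |
| Normal | 5% | +1.15 | 0.537 | 0.510 | +5.3% | 85.0% | 88.7% |
| Skewed | 1% | +0.40 | 0.521 | 0.503 | +3.5% | 91.5% | 92.0% |
| Skewed | 2% | +0.79 | 0.570 | 0.541 | +5.4% | 88.5% | 91.0% |
| Skewed | 5% | +1.95 | 0.693 | 0.647 | +7.0% | 64.5% | 73.8% |

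With nobody filled, the two orders agree. These powers should not be read against the planned 90%, which comes from an unadjusted t-test; the simulated ANCOVA gains from the assumed baseline correlation.

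**4. Effect on the treatment difference.** Equal fills of 5%: −1.60 against −1.61 (normal), −1.63 against −1.66 (skewed). With 2% active and 5% placebo: −2.26 against −2.19, and −2.67 against −2.59. With the fractions reversed: −1.03 against −1.10, and −0.80 against −0.91.

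**5. Null case.** With no true difference, 5% filled in both arms, skewed scores and 1,000 trials, rejection was 3.3% under the SAP order and 3.6% reversed.

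**6. Share due to the order.** Normal scores: SE is 0.422 with no fills, 0.510 with 5% filled after MI, and 0.537 with 5% filled before. Of the total growth of 0.115, the fill itself accounts for 0.088 and the order for 0.027.

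**The case against.** The best defence is that under a composite strategy the worst value is the outcome. A patient lost before week 48 might later have had the event, so modelling the composite outcome for that patient is reasonable. This stands for ICE 3b, which Table 4 labels composite. It does not cover the adverse-event and lack-of-efficacy fill, which Table 4 lists as a missing-data rule. Nor does it cover ICE 4 and long travel (ICE 5b), where a hypothetical strategy targets the value without the event.

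A second objection is that few patients may be filled. That stands as a limit on size. The route requires leaving the study, not merely stopping drug, and having no score at all in weeks 48-60. Patients who stop drug are encouraged to stay (protocol 8.3.2), and their data are used.

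A reader might also infer three stronger things that the documents do not support:

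- That the primary comparison is invalid. With equal fills the difference is almost unchanged, and the equal-fill null case showed no inflation.
- That the fall to about 65% power in the harshest scenario is due to the order. Reversing it recovers only to about 74%; the rest comes from the worst-score rule.
- That all of the planned 20% dropout, less those filled, would receive distorted values. That rate is by week 60, and patients who leave during weeks 48-60 with diary entries need no imputation. The simulation's 20% with no data is therefore towards the high end.

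**Conclusion.** The point holds as a loss of efficiency and a mislabelled reference analysis. The SAP states the order, nothing keeps the filled values out of the model, and the result is inconsistent with the missing-at-random description at δ=0.

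For 1-5% filled per arm, under the assumptions listed, the order alone raises imputed values by about 0.2-2.0 points, against a planned effect of 1.8. It widens the primary standard error by about 2-7%. The cost in power runs from about 1 point or less at 1% filled to about 4-9 points at 5%. If fills differ between arms (2% against 5%), the treatment difference moves by about 0.07-0.12 points, exaggerating the effect when placebo has more fills and diluting it when active has more.

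The direction is certain whenever the arm-worst average lies above what the model would predict. The size is not, because the filled fraction, the score distribution and the correlations are all assumed. This should be fixed, but it does not undermine the trial.

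**What to change.** In SAP 5.6.1, replace the sentence on order. Run MI Steps 1 and 2 with the weeks 48-60 averages of adverse-event and lack-of-efficacy leavers and ICE 3b patients left out of the model. Then write the arm-worst value, taken from observed averages, into each of the 50 completed data sets before the ANCOVA and MIANALYZE steps.

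State whether ICE 3a averages, which are part observed and part own-worst, enter the imputation model; the present sentence covers them too. Apply the same order to the tipping-point analysis and to the daily-score endpoints that follow Table 4 (TNSS, TSS, TOSS, DMS and the asthma daily symptom score). Correct the second PROC MI variable list at the same time.

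If the sponsor prefers to keep the present order, the weaker alternative is to pre-specify the reversed order as a sensitivity analysis and to reword the description of δ=0.

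The cost is a short SAP edit before unblinding and a re-ordered program step. It needs no extra data or patients, and the penalty for failures is unchanged.

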3.1. The Full Analysis Set (FAS)

The full analysis set (FAS) includes all randomized patients; it is based on the treatment allocated (as randomized). Efficacy endpoints will be analyzed using the FAS.

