Primary endpoint	Daily combined symptom and medication scores (CSMS) averaged over the last 12 weeks of the treatment period	FAS	
The intercurrent events will be handled as follows¹:
 
 1. Discontinuing the study intervention: all data collected after discontinuation will be used in the analysis (treatment policy strategy) 2. Rescue treatment and select prohibited medications^{2,3} taken to treat allergic symptoms during the last 12 weeks of the efficacy assessment period: data after medication will be used in the analysis (treatment policy strategy) 3. Prohibited medications taken during the efficacy assessment period which are adjudicated to be handled using a composite strategy³: 
 a. The daily CSMS, starting from the day the prohibited medication was taken through the end of the last 12 weeks of efficacy assessment, will be imputed by worst CSMS score (largest observed TNSS+TOSS+DMS) observed before prohibited medications were taken from the same patient. The average CSMS will be calculated using observed components prior to receiving prohibited medication and imputed values after prohibited medication. b. If no values of CSMS⁴ are available during the last 12 weeks of the efficacy assessment period prior to the patient taking prohibited medication, the daily CSMS will be imputed using the worst average CSMS score during the last 12 weeks of all observations in the corresponding treatment group 4. Prohibited medications taken during the efficacy assessment period which are adjudicated to be handled using a hypothetical strategy³: data during use of medication and during washout period will be set to missing 5. Change in cat allergen exposure: 
 a. If no cat is living in the patient's home during all or part of the last 12 weeks of the treatment period: all available data will be used in analysis (treatment policy) b. If patient travels away from home for less than 42 consecutive days: all available data will be used in 	
ANCOVA model with treatment group, stratification factors, and cat sIgE (<17.5 kUa/L versus \geq17.5 kUa/L) as fixed factors and baseline CSMS as a covariate.
 
The least squares means (LS-means) estimates for the average CSMS during the last 12 weeks of the treatment period for each treatment group, as well as the difference between the REGN1908-1909 and placebo will be provided along with the corresponding 2-sided p-value and associated 95% confidence interval.

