Each imputed data set will then be analyzed by ANCOVA as previously described. The SAS procedure PROC MIANALYZE will be used to generate valid statistical inferences by combining results from these 50 ANCOVA analyses using Rubin's formula. The least squares means (LS-means) estimates for the average CSMS during the last 12 weeks of the treatment period for each treatment group, as well as the difference between the REGN1908-1909 and placebo will be provided along with the corresponding 2-sided p-value and associated 95% confidence interval.

Sensitivity analysis:

With respect to the missing data handling of daily entries, sensitivity analyses will be performed to confirm robustness of the conclusion drawn based on the main model for primary analysis.

Tipping Point Analysis

Sensitivity analysis using a tipping point approach with MI will be performed to assess the robustness of the results due to data that may be missing not-at-random (MNAR). The impact from missing data on comparisons of average CSMS during the last 12 weeks between REGN1908-1909 and placebo will be examined.

This approach will introduce a sensitivity parameter, δ . Estimations will be performed using MI methodology. Missing data will be imputed 50 times to generate 50 complete data sets utilizing the SAS procedure PROC MI for each δ following the 2 steps as previously described, where δ will be added to each of the imputed values (of average of last 12 weeks) for patients in the REGN1908-1909 arm. (Note that when $\delta=0$, this aligns with the standard MI analysis assuming missing at random (MAR).) Scores that are adjusted to outside the range of CSMS will be truncated in the same manner as previously described for the MI method.

Each imputed data set will then be analyzed by ANCOVA as previously described. For each δ , the SAS procedure PROC MIANALYZE will be used to generate valid statistical inferences by combining results from these 50 ANCOVA analyses using Rubin's formula. By progressively increasing δ , the sensitivity analysis will explore the “tipping point”, where the result is no longer statistically significant (i.e., $p\text{-value}>0.049$).

Additional Sensitivity Analyses

An additional sensitivity analysis may be performed when determining asthma status from medical history and house dust mite sensitization status from lab data, rather than as stratified.

Supplemental Analyses

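### SAP 5.6.1: the sample code for MI Step 2 omits the week 48–60 CSMS from its variable list, so as printed it does not carry out the Step 2 text

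*SAP*

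**What the plan says.** The primary analysis is an ANCOVA on the FAS, and SAP 3.1 states that "The full analysis set (FAS) includes all randomized patients". SAP Table 4 sorts patients who have no CSMS value in weeks 48–60. Those who left the study for adverse events or lack of efficacy get a worst score. For the rest, "Missing data due to any other reason will be imputed using MI". Table 4 can also create missing days. Under the hypothetical strategy for some prohibited medications, "data during use of medication and during washout period will be set to missing", and long travel away from home is treated in the same way.

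SAP 5.6.1 then describes the MI. Worst-score imputation comes first. After that, "missing data (the average CSMS) will be imputed 50 times to generate 50 complete data sets". Step 1 uses MCMC by treatment group to fill the weeks 0–12 average only, so that the pattern becomes monotone. In Step 2, "missing values of average CSMS from weeks 48-60 will be imputed using a monotone regression method", with the ANCOVA covariates and the weeks 0–12 average as predictors. Inference comes from "combining results from these 50 ANCOVA analyses" by Rubin's formula. The tipping-point analysis repeats the two steps and adds a shift, delta, to the imputed week 48–60 averages in the REGN1908-1909 arm.

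Sample SAS code follows the text. The Step 1 call has the list "var BASELINE CSMS012 CSMS4860" and the option impute=monotone. The Step 2 call has the list "var TRTP STRAT1 STRAT2 STRAT3 CATIGE BASELINE CSMS012" and a monotone regression statement that names no target variable.

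**The concern.** PROC MI imputes only variables in its VAR list. The Step 2 list stops at CSMS012, the weeks 0–12 average, so the step whose purpose is to impute the primary endpoint does not contain that endpoint. Code and text sit on the same page and specify different things.

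A programmer who copied the printed list would get an ANCOVA on observed and worst-score values only, which is not the analysis the text describes. The tipping-point analysis is the SAP's named check on data missing not at random. It would then say nothing about the MI patients, and delta would leave their contribution unchanged however large it was. SAP 5.6.2 gives the averaged symptom and medication scores the same missing-data strategy, so a reused template would carry the omission to them.

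**Working it through.** **1. The plan's own size, as background.** SAP 2.3 gives a difference of 1.8, SD 6.2, two-sided alpha 0.049 and 90% power. The standardized difference is 1.8/6.2 = 0.290. A two-sample t-test then needs 251.6 per arm, and power at 251 per arm is 89.9%. This reproduces the stated 251 and 90%. Dividing by 0.8 gives 251/0.8 = 313.75, so 314, against the stated 315 (315 − 251 = 64). The 251 already excludes the dropouts, so planned power does not rely on MI patients.

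**2. Trace of the printed code.**
- *Step 1.* The variable order is BASELINE, CSMS012, CSMS4860. With impute=monotone, PROC MI fills only values that break the monotone order: CSMS012 where CSMS4860 is observed. A missing value in the last variable never breaks that order, so CSMS4860 is not filled. This agrees with the Step 1 text.
- *Step 2.* CSMS4860 is not in the list. The only values left to fill are CSMS012 in patients who lack both periods.
- *ANCOVA.* The outcome is CSMS4860, still missing for MI patients, so they are excluded. CSMS012 is not in the model, and SAP 6.2 fills missing baselines with one fixed average. The 50 data sets therefore give the same fit.

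**3. Mechanical check on synthetic data.** Two simulated trials of 630 patients (315 per arm), with 50 imputations each. A regression draw stands in for MCMC in Step 1.

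| | Trial A, printed | Trial A, corrected | Trial B, printed | Trial B, corrected |
|---|---|---|---|---|
| Week 48–60 values missing | 116 | 116 | 136 | 136 |
| Filled | 0 | 116 | 0 | 136 |
| Patients in ANCOVA | 514 | 630 | 494 | 630 |
| Between-imputation variance | 0 | 0.016 | 0 to rounding | 0.039 |
| Change in estimate at delta = 5 | 0.00 | 0.90 | not run | not run |

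In trial A, 97 patients lacked weeks 48–60 only and 19 lacked both periods: 97 + 19 = 116 and 630 − 116 = 514. In trial B, 630 − 136 = 494. Correlations, baseline means and missingness were assumed, and trial A left the strata and sIgE out of its ANCOVA. Only the pattern carries over, not the values.

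**4. What delta can do.** Before truncation to 0–38, one unit of delta moves the treatment difference by about m/315, where m is the number of MI patients in the drug arm. With corrected code, m = 16, 32 and 64 give 16/315 = 0.05, 32/315 = 0.10 and 64/315 = 0.20. In trial A, 0.90 × 315/5 = 56.7, so m was about 57. With the printed list the movement is 0 for every m.

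The documents do not give m. If dropout is the planned 20%, m lies between 0 and about 64, depending on how many leave for adverse events or lack of efficacy. That is a range and not a bound. Data set to missing for medication or travel can add patients, and patients who stop drug but stay in the study reduce the number.

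**The case against.** The strongest reply is that nothing in the planned method is wrong. The Step 2 text names the target, the method and the predictors. The block is labelled as sample syntax and is not a full program: the truncation to 0–38 required by the text is not coded. The tipping-point section refers back to the two steps, which the text describes in full. All of this stands. A reader might infer that the SAP plans a primary analysis without MI, and the documents do not support that.

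Second, the failure would not be silent. A reduced ANCOVA sample, zero between-imputation variance and an estimate that ignores delta would all show in routine output. This stands too, and it makes an unnoticed effect on the primary result unlikely.

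Third, the PDF reading may have lost a word. Two option names in the same block are visibly garbled. This cannot be excluded. It is not the likelier explanation, because the garbling is inside words, the Step 2 line is whole to its semicolon, and the same variable name survived in the Step 1 list.

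A reader might also infer a bias of some stated size in the primary estimate. The documents do not give the dropout pattern, the number of MI patients or the correlations between periods, so any figure would reflect assumed inputs.

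**Conclusion.** The sample code for MI Step 2 does not implement the Step 2 text. Run as printed, it would multiply impute none of the week 48–60 averages. The primary ANCOVA would lose every MI patient, the 50 fits would coincide, and delta would have no multiply imputed value to shift. This follows from how PROC MI treats its variable list and the monotone option, and both synthetic trials show it.

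The conclusion rests on the printed list being what the original page shows. Worst-score patients are handled before MI and are unaffected. The effect on the primary estimate cannot be quantified: about zero if dropout is random or depends on earlier scores equally in both arms, and in either direction otherwise.

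This is a minor correction to sample code, and confidence is medium until the original page has been seen.

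**What to change.** Look at the original SAP page first. If the variable name is there, nothing needs changing. If it is absent:

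- Extend the Step 2 list, now "var TRTP STRAT1 STRAT2 STRAT3 CATIGE BASELINE CSMS012", by adding CSMS4860 as its last variable.
- Sort by _imputation_ before Step 2, because Step 1 runs by treatment group and Step 2 by imputation number.
- Use the corrected code for the tipping-point runs and for any secondary endpoint that reuses it.

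The cost is one variable name and one sort step. The method, sample size and timetable do not change.
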